### 4.3. Final Analysis

An unblinded analysis of the efficacy data will occur after all study participants have completed the study. The data will be cleaned, frozen, and a blinded data review will take place. Subsequently, data will be locked, protocol deviations will be adjudicated, and study populations will be defined before breaking the study blind.

## 5. Analysis Populations

The following analysis populations are planned for this study:

- **Randomized Population (RAND):** The randomized population includes all participants who were randomized.
- **Enrolled Population (ENRL):** The enrolled population includes all participants who sign the informed consent form.
- **Safety Population (SAF):** The safety population includes all participants randomly assigned to study intervention and who take at least one partial or full dose of study intervention. Participants will be analyzed according to the intervention they actually received.
- **Intent-To-Treat Population (ITT):** The ITT population includes all participants who were randomized and have at least one postbaseline efficacy assessment. Participants will be analyzed according to the intervention they were randomized to.
- **Modified Intent-To-Treat Population (MITT):** The MITT population includes all participants in the ITT population who have at least one efficacy assessment after the Day 90 dosing visit.
- **Evaluable Population (EVAL):** The evaluable population includes all participants who received 6 full doses of study intervention and completed the study.

- **Pharmacokinetic Population (PK):** The PK population includes all participants in the safety population without major dosing violations. Details will be provided in the PKAP.
- **Per-Protocol Population (PP):** The PP population includes all participants who were randomized and had no major protocol deviations that affect efficacy endpoint assessment as adjudicated by the sponsor.

The primary and the key secondary efficacy analyses will be performed on the MITT population and repeated in further analysis populations as described in section 8.

## 6. General Issues for Statistical Analysis

### 6.1. Statistical Definitions and Algorithms

#### 6.1.1. Study Day

Study Day 1 is defined as the first dose date (i.e., date of first administration of randomized study intervention). The first dose date is used as the reference start date for analysis.

For days prior to Study Day 1:

Study Day = reference date – first dose date.

For days on or following Study Day 1, Study Day = reference date – first dose date + 1.

#### 6.1.2. Baseline

Post baseline assessments will be those assessed after the date/time of the first dose.

For all  $AUC_{24\text{-hour } U_{ox}}$  endpoints, the baseline is an average of the two 24-hour  $U_{ox}$  Screening results.

For the remaining endpoints, the last observation recorded prior to the first dose of study intervention will be used as the baseline observation for all calculations of change from baseline.

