3. OBJECTIVES AND ENDPOINTS

Objectives	Endpoints
Primary	
To assess the efficacy of DCR-PHXC in reducing urinary oxalate burden in patients with PH	AUC from Day 90 to Day 180, based on percent change from Baseline in 24-hour Uox
Key Secondary	
To identify the proportion of participants with normalized or near-normalized Uox	The proportion of participants with a 24-hour Uox level < 0.46 mmol/24 hours or ≥ 0.46 to < 0.60 mmol/24 hours (adjusted per 1.73 m ² BSA in participants aged < 18 years) on at least 2 consecutive visits, beginning with Day 90
Secondary	
1. To evaluate the effect of DCR-PHXC on stone burden in patients with PH	1. Percent change in the summed surface area and number of kidney stones identified via kidney ultrasound from Baseline to Day 180
2. To evaluate the effect of DCR-PHXC on plasma oxalate in patients with PH	2. Percent change in plasma oxalate from Baseline to Day 180 (for adults only)
3. To evaluate the effect of DCR-PHXC on eGFR	3. Rate of change in eGFR from Baseline to Day 180
4. To assess the safety of DCR-PHXC in patients with PH	4. AE and SAE; change from Baseline in 12-lead ECG, physical examination findings, vital signs, and clinical laboratory tests
5. To characterize the PK of DCR-PHXC in patients with PH	5. Population and individual PK parameters for DCR-PHXC
Tertiary/Exploratory	
1. To evaluate the effect of DCR-PHXC on stone events in patients with PH	1. Number of stone events over a 6-month period
2. To assess the efficacy of DCR-PHXC in reducing Uox burden over 6 months in patients with PH	2. AUC of 24-hour Uox from Day 1 to Day 180, based on percent change from Baseline
3. To assess the efficacy of DCR-PHXC in reducing Uox at month 6 in patients with PH	3. Percent change in 24-hour Uox from Baseline to Day 180
4. To evaluate the effect of DCR-PHXC on urinary oxalate-to-creatinine ratio in patients with PH	4. AUC of 24-hour urinary oxalate-to-creatinine ratio from Day 90 to Day 180, based on percent change from Baseline
5. To evaluate the effect of DCR-PHXC on QoL Assessments in patients with PH	5. Change from Baseline to Day 180 in the SF-36 and EQ-5D-5L in adults; and in the PedsQL™ in children
6. To evaluate the relationship between Uox spot urine and 24-hour urine measurement in patients with PH	6. Uox in spot urine and 24-hour urine

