8. STUDY ASSESSMENTS AND PROCEDURES

8.1. EFFICACY ASSESSMENTS

8.1.1. 24-Hour Urinary Oxalate

Oxalate is a dicarboxylic acid that is a normal end-product of metabolism. Most oxalate in the body is produced in the liver. Humans lack an enzyme to degrade oxalate, and thus it must be eliminated by the kidney. In individuals with PH, mutations in the *AGXT* or *GRHPR* gene result in the overproduction of oxalate by the liver, which causes increased oxalate excretion by the kidneys.

The measurement of oxalate in the urine will be via 24-hour urine collection. During the screening period, participants will perform two 24-hour urine collections at home. The oxalate level in both collections must be ≥ 0.7 mmol (adjusted per 1.73 m^2 BSA in those younger than 18 years) for a participant to be eligible for study entry. Note that 12 of the participants enrolled must have at least one 24-hour Uox excretion value ≥ 1.6 mmol. There must be less than a 20% variation between the 2 urinary creatinine excretion values obtained in the screening collections for a participant to be eligible for study entry (see Section 8.1.1.1.1). Potential participants will be allowed a second attempt at achieving a less than a 20% variation should the first pair of measurements differ by more than 20%.

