#### 6.1.3. Adjustments for Covariates

Statistical models based on  $U_{ox}$  results will include covariates for age category [6 to 11, 12 to 17, or  $\geq 18$  years] and eGFR category [ $< 45$  mL/min or  $\geq 45$  mL/min]. The baseline for the endpoint being analyzed will be included as a covariate.

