### Area Under the Curve (AUC)

AUC24-hour Uox is calculated based on the percent change from baseline in Uox. The x-axis will be time in days and y-axis will be percent change from baseline in Uox. A percent decrease from baseline in Uox will be denoted as negative. A percent increase from baseline in Uox will be denoted as positive. The curve might be in its entirety, or at least in part, below the x-axis (Panel A, Figure 1). The area below the x-axis will be calculated and presented as a positive value. For an increase from baseline the percent change from baseline will be positive and that part of curve will be above the x-axis. The AUC would then be calculated as area below the axis minus area above the x-axis (Panel B, Figure 1). The AUC will be calculated using the trapezoidal rule; however, given that the percent change from baseline in Uox can change sign, we will use the approach outlined in the PharmaSUG by Jianfeng Ye.

The AUC will be calculated using the actual time in days between Uox collections, and not the nominal visit days. See Figure 1 for examples of the AUC, where the portion of the data to be used in calculation of the primary endpoint is contained within the orange box.

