#### 8.4. Tertiary/Exploratory Efficacy Analysis

The same statistical model described above for the primary efficacy analysis will be applied to the following tertiary/exploratory efficacy endpoints.

- AUC24-hour Uox from Day 1 to Day 180, based on percent change from baseline (ITT population)
- Percent change in 24-hour Uox from baseline to Day 180 (ITT population)
- AUC24-hour Uox:creatinine from Day 90 to Day 180, based on percent change from baseline (MITT population)
- Change from baseline to Day 180 in the SF-36, EQ-5D-5L in adults, and in the PedsQLTM in children (ITT population)

The number of stone events over a 6-month period will be analyzed using an exact Poisson regression model. The model will include treatment group and baseline stone events rate (continuous). Baseline stone events rate will be the number of stone events observed over the past 12 months prior to dosing. The model will include an offset term for total follow-up time as the 'number of months exposed' equal to the total elapsed time between first dose date and last day of visit in the study, divided by 30.4375. Annualized stone event rate (number of stone events per year per person) will be derived as number of stone events in the exposure period / total number of years exposed.

Example SAS code is given below:

```
PROC GENMOD DATA=;  
  CLASS TREATMENT;  
  MODEL 'Number_stone_evts_6month'=Treatment Kidney_Stone_Event_Baseline  
/OFFSET=Ln_Number_Of_Months_Exposed DIST=POISSON LINK=LOG DSCALE;  
  EXACT Treatment Kidney_Stone_Event_Baseline / ESTIMATE;  
RUN;
```

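### The exploratory Day 180 percent change in 24-hour Uox takes only the last screening collection as baseline, while the AUC endpoints use the mean of two

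*SAP*

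**What the plan says.** SAP 6.1.2 has two baseline rules. For the AUC endpoints of 24-hour Uox, "the baseline is an average of the two 24-hour" Uox screening results. After that, "For the remaining endpoints, the last observation recorded prior to the first dose of study intervention will be used as the baseline observation".

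Protocol section 3 lists the endpoint in question as "Percent change in 24-hour Uox from Baseline to Day 180". SAP 2.2.2.4 and 8.4 list it as an exploratory endpoint separate from the AUC endpoints, so the second rule applies to it.

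Protocol 8.1.1 supplies the pre-dose data: "During the screening period, participants will perform two 24-hour urine collections at home". The schedules of activities in both documents mark no 24-hour Uox collection on Day 1, so the last pre-dose observation is the later screening collection.

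For the analysis, SAP 8.4 says "The same statistical model described above for the primary efficacy analysis will be applied to the following tertiary/exploratory efficacy endpoints", and SAP 6.1.3 says "The baseline for the endpoint being analyzed will be included as a covariate". SAP 6.1.9 builds the AUC from visit-level values: it "is calculated based on the percent change from baseline in Uox".

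**The concern.** A single 24-hour urine collection is a noisy measurement, and a percent change puts that noise in the denominator. Every participant provides two screening collections, and the primary endpoint uses both. Dropping one for the Day 180 endpoint gives up precision in a trial planned with 24 active and 12 placebo participants.

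There is also an inconsistency. The same Day 180 urine sample gives one percent change inside the AUC calculation and another as the Day 180 endpoint. The two agree only when a participant's two screening Uox values are equal. The screening rule in Protocol 8.1.1.1.1 limits variation in creatinine, not in Uox, so differences should be expected. Someone checking the Day 180 result against the data behind the primary endpoint would find values that do not match.

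**Working it through.** **The plan's own figure.** The documents give no power or precision for the Day 180 endpoint. The only power figure, about 94% in Protocol 9.2, concerns the primary AUC. With effect size 1.2, 24 against 12 participants and one-sided 0.025, the normal approximation gives 1.2 × √(24 × 12 / 36) = 3.39; 3.39 − 1.96 = 1.43; power 92.4%. A noncentral t on 34 degrees of freedom gives 90.9%. Neither bears on this point.

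**Step 1: the two denominators.** Let b1 and b2 be the screening values and y the Day 180 value.
- Day 180 point of the AUC: 100 × (y / [(b1 + b2)/2] − 1)
- Day 180 endpoint: 100 × (y / b2 − 1)

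Illustrative values: b1 = 1.4, b2 = 1.8, y = 0.9 mmol.
- AUC point: 0.9/1.6 − 1 = −43.8%
- Endpoint: 0.9/1.8 − 1 = −50.0%
- Endpoint with the screening order reversed: 0.9/1.4 − 1 = −35.7%

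**Step 2: within-person precision.** Assume each collection has the same error variance s² on the log scale, with independent errors.
- One baseline: s² + s² = 2s²
- Mean of two (approximately): s² + s²/2 = 1.5s²
- SD ratio: √(1.5/2) = 0.866, a cut of about 13%. Equivalently, the single baseline carries 33% more variance (2/1.5) and a 15% larger SD.

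If the two screening errors have correlation ρ, the mean-of-two variance becomes s²[1 + (1 + ρ)/2]. At an assumed ρ = 0.5 this is 1.75s², and 1 − √(1.75/2) = 6.5%.

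**Step 3: standard error of the treatment difference.** The documents give neither a within-person CV for Uox nor the spread of true response, so both are assumed. The simulation used 24 against 12 participants, a 40% reduction on active, log-normal errors independent across collections, a between-person baseline CV of 40%, and 6000 runs per scenario. Each percent change was analysed by ANCOVA on treatment and its own baseline; age and eGFR category were omitted. SEs are in percentage points.

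| Within-person CV | SD of log response | SE, mean of two | SE, last only | Ratio |
|---|---|---|---|---|
| 10% | 0 | 3.88 | 4.49 | 1.157 |
| 10% | 0.2 | 7.47 | 7.82 | 1.047 |
| 10% | 0.3 | 10.51 | 10.83 | 1.030 |
| 20% | 0 | 7.90 | 9.11 | 1.153 |
| 20% | 0.2 | 10.24 | 11.36 | 1.109 |
| 20% | 0.3 | 13.06 | 14.10 | 1.080 |
| 30% | 0 | 12.05 | 14.21 | 1.179 |
| 30% | 0.2 | 13.92 | 15.88 | 1.141 |
| 30% | 0.3 | 15.99 | 17.95 | 1.123 |

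The single baseline makes the SE 3% to 18% larger (variance 6% to 39% larger). At 30% CV with no response heterogeneity the ratio exceeds the log-scale 1.155, because percent change is skewed by a noisy denominator. Within each CV, the penalty shrinks as true responses spread out.

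**Step 4: typical mismatch.** At an assumed CV of 20%, the median absolute gap between a participant's two Day 180 values is about 5 percentage points on active and 9 on placebo.

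**The case against.** The last pre-dose value is a conventional default, and the endpoint carries no alpha: it is exploratory and absent from the sequence in SAP 6.1.4. SAP 8.4 carries over the primary model, so one might say that the primary baseline comes with it. That does not hold. A model is not a baseline definition, and SAP 6.1.3 ties the covariate to the endpoint's own baseline. The mean-of-two definition in Protocol 8.1.1.1.1 and SAP 6.1.5.2 sits in the creatinine completeness text and does not override 6.1.2 for Uox.

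The objection to the size is stronger. The 13% is a within-person figure. Protocol 8.1.1.1 asks for the screening collections on consecutive days, so diet and hydration may affect both and correlate their errors. Response heterogeneity reduces the gain further. Both qualifications stand.

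Two wider inferences are tempting but not supported:
- **The oxalate-to-creatinine AUC also drops to one baseline.** SAP 6.1.2 does not name the ratio, but SAP 6.1.9 says that this AUC is calculated as for Uox apart from the variable. Its baseline is unconfirmed; it has not been shown to be the single value.
- **The by-visit tables will disagree with the primary.** SAP 8.1 promises by-visit percent changes without naming a baseline. They sit in the primary analysis section and may well share its baseline.

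**Conclusion.** The point holds for one exploratory endpoint. On the text of SAP 6.1.2, percent change in 24-hour Uox at Day 180 uses the later screening collection alone as baseline and covariate. That wastes a measurement already taken and makes the endpoint differ from the Day 180 point of the AUC.

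Under independent, equal errors the within-person SD falls by about 13% with averaging. Over the assumed ranges, the standard error of the treatment difference is 3% to 18% larger with the single baseline; these figures depend on variability that the documents do not state. Correlated screening errors would reduce the gain.

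A reader might infer that the primary result is weakened. It is not: the primary AUC already uses the two-collection mean, and SAP 8.5 tests that choice with the lower of the two values. This is a minor improvement in precision and consistency, not a threat to the trial's conclusion.

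**What to change.** Add one sentence to SAP 6.1.2 after the AUC rule:

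> For percent change in 24-hour Uox at Day 180, and for the by-visit percent-change summaries of 24-hour Uox, baseline is the mean of the two screening collections, as for the AUC endpoints.

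The covariate then follows through SAP 6.1.3. In the same edit, confirm that the oxalate-to-creatinine AUC also takes the two-collection mean. Leave the existing wording of the primary endpoint's baseline unchanged, so that a repair to an exploratory endpoint does not redefine the primary one.

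The change needs no new data and alters no confirmatory test. It should be made before database lock and unblinding. If the single-value baseline was intended for Day 180, the SAP should say so and give the reason.

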#### 6.1.3. Adjustments for Covariates

Statistical models based on  $U_{ox}$  results will include covariates for age category [6 to 11, 12 to 17, or  $\geq 18$  years] and eGFR category [ $< 45$  mL/min or  $\geq 45$  mL/min]. The baseline for the endpoint being analyzed will be included as a covariate.

### 6.1.5. Handling of Dropouts or Missing Data

#### 6.1.5.1. Missing Efficacy Endpoint Data

While all possible efforts will be made to ensure that participants stay in the study and all data is collected as scheduled, the occurrence of missing data cannot be completely eliminated.

For the analysis of AUC related efficacy endpoints, based on the MITT or ITT populations, a multiple imputation (MI) approach under the missing-at-random (MAR) assumption will be used to handle missing endpoint data. Subsequently, the AUC related efficacy endpoints will be calculated.

That is, any participant who withdraws or is discontinued from the study or who misses a scheduled visit or assessment through Day 180 will have their missing AUC related efficacy data analyzed as imputed using MI techniques.

Multiple imputation based on a standard MAR imputation approach will be performed in SAS® software using the general approach described below. This strategy is appropriate for data sets that have an arbitrary missing data pattern.

*Step 1:* The Missing at Random (MAR) imputation model will impute missing values using a fully conditional specification (FCS) regression-based multiple imputation model. For participants with missing data at a particular visit, a multiple regression model will be fit that includes the outcome at that visit as the dependent variable and observed data (e.g., outcomes at other visits, treatment, age category [6 to 11, 12 to 17, or ≥18 years], eGFR category [<45 mL/min or ≥45 mL/min], and baseline value of the primary response variable (e.g., Uox or Uox-to-creatinine ratio) as independent variables. This process will be repeated 50 times, resulting in 50 complete analysis data sets. The seed number of 3216549 will be used for the imputation procedure described in Step 1.

SAS pseudo code is provided below:

```
PROC MI DATA=indata OUT=outdata SEED=3216549 NIMPUTE=50;  
  CLASS <treatment> <age category> <eGFR category>;  
  FCS REG (<day 90> <day120> <day 150> <day 180>);  
  VAR <treatment> <age category> <eGFR category> <baseline> <day 90> <day120>  
    <day 150> <day 180>;  
RUN;
```

*Step 2:* The corresponding derived efficacy endpoints (e.g.,  $AUC_{24\text{-hour } U_{ox}}$  from Day 90 to Day 180) will be calculated based on the imputed data for each participant and for each of the completed analysis datasets. The standard SAS code that is developed to calculate the derived efficacy endpoints (e.g.  $AUC_{24\text{-hour } U_{ox}}$  from Day 90 to Day 180) will be applied to each of the 50 imputed datasets.

*Step 3:* The ANCOVA analyses will be performed separately for each of the 50 completed analysis data sets, and the results will be combined into one multiple imputation inference (estimated treatment effect, standard error, p-value and associated 95% CI) using the SAS MIANALYZE procedure. The treatment difference will be tested at the one-sided 2.5% level and corresponding 95% CIs will be calculated. SAS Note: As PROC GLM does not report standard error for the difference of two LSMeans, GLM cannot be used in conjunction with PROC MIANALYZE. However, the equivalent code using PROC MIXED can be used to obtain the combined results.

SAS pseudo code is provided below:

```
PROC SORT DATA=outdata1 OUT=efficacydat;  
  BY <imputation number> <treatment>;  
RUN;
```

```
PROC MIXED DATA=efficacydat;  
  BY <imputation number>;  
  CLASS <treatment> <age category> <eGFR category>;  
  MODEL <efficacy variable> = <treatment> <age category> <eGFR category>  
    <baseline> ;  
  LSMEANS <treatment> / DIFF;  
  ODS OUTPUT LSMeans=lsmeans_ds Diffs=diffs_ds;  
RUN;
```

```
*COMBINES THE LS MEANS ACROSS THE MI DATASETS;  
PROC SORT DATA=lsmeans_ds;  
  BY <treatment> <imputation number>;  
RUN;
```

```
PROC MIANALYZE DATA=lsmeans_ds;  
  BY <treatment>;  
  MODELEFFECTS estimate;  
  STDERR stderr;  
RUN;
```

```
*COMBINES THE LS MEAN DIFFERENCES ACROSS THE MI DATASETS;  
PROC SORT DATA=diffs_ds;  
  BY <treatment> <imputation number>;  
RUN;
```

```
PROC MIANALYZE DATA=diffs_ds;  
  BY <treatment>;  
  MODELEFFECTS estimate;  
  STDERR stderr;  
RUN;
```

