| Urine drug screen h                | X                         |           |   |            |            |                 |            |            |            |             |             |             |    |
| Viral serology i                   | X                         |           |   |            |            |                 |            |            |            |             |             |             |    |
| FSH (postmenopausal women)                    | X                         |           |   |            |            |                 |            |            |            |             |             |             |    |
| Study intervention administration             |                           | X         |   |            | X          |                 |            | X          | X          | X           | X           |             |    |
| Spot urine collection j            | X                         |           |   |            | X          |                 |            | X          | X          | X           | X           | X           | X  |
| 24-hr urinary oxalate k            | X                         |           |   |            | X          |                 |            | X          | X          | X           | X           | X           | X  |
| 24-hr urinary creatinine l         | X                         |           |   |            | X          |                 |            | X          | X          | X           | X           | X           | X  |
| Blood draw for vitamin B6 levels m |                           | X         |   |            | X          |                 |            | X          | X          | X           | X           | X           |    |
| Plasma PK sample n                 |                           | X         | X |            | X          | X               |            |            |            |             | X           |             | X  |
| Plasma oxalate sample o            | X                         | X         |   |            | X          |                 |            | X          | X          | X           | X           | X           | X  |
| Record fluid intake p              | X                         | X         |   |            | X          |                 |            | X          | X          | X           | X           | X           |    |

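### The coded imputation model leaves out Day 30 and Day 60 Uox, against the SAP's own prose; this touches the ITT sensitivity analysis and the exploratory Day 1–180 AUC

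*SAP*

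**What the plan says.** - **Collection.** The row "24-hr urinary oxalate" in SAP Table 1 schedules Uox at screening, Days 30, 60, 90, 120, 150 and 180, and early termination.
- **Code.** SAP 6.1.5.1 specifies "FCS REG (<day 90> <day120> <day 150> <day 180>". The VAR list holds the same four visits plus treatment, age category, eGFR category and baseline. The placebo-based statement in SAP 8.5 uses the same four visits.
- **Prose around the code.** Predictors are "observed data (e.g., outcomes at other visits, treatment, age category" and so on, with no restriction to Day 90 onward. Any participant "who misses a scheduled visit or assessment through Day 180 will have their missing AUC related efficacy data analyzed as imputed using MI techniques". The method is introduced as "using the general approach described below", and the code is labelled pseudo code.
- **Where imputation applies.** "For the analysis of AUC related efficacy endpoints, based on the MITT or ITT populations". SAP 6.1.5.2 treats collections that fail the completeness criteria as missing and sends them to the same procedure.
- **Populations.** "The ITT population includes all participants who were randomized and have at least one postbaseline efficacy assessment" (SAP 5). MITT also requires an efficacy assessment after the Day 90 dosing visit. The primary analysis uses MITT; ITT is a sensitivity analysis (SAP 8.5).
- **Exploratory endpoint.** SAP 8.4 lists the AUC "from Day 1 to Day 180, based on percent change from baseline (ITT population") and gives no imputation code of its own for it.
- **Protocol.** Section 9.1 treats the AUC as missing when there is no Uox after the Day 90 visit.

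**The concern.** The code and the prose describe two different imputation models, and the choice changes results in two places.

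First, the ITT analysis exists to bring back participants whom MITT drops. Some of them may have on-treatment Uox from Days 30 and 60 only. Under the code, those values play no part in imputing Days 90 to 180. Missing at random is most credible when the model conditions on observed outcomes that may be related to leaving. Here it would discard the only on-treatment outcomes such a participant has.

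Second, the Day 1–180 AUC uses Day 30 and Day 60 directly. Under the code, a missed or invalid collection at either visit stays missing, although the prose says it will be imputed.

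The SAP fixes the seed and the number of imputations, so the variable list should be equally unambiguous before database lock.

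**Working it through.** **Planning figures (SAP 3.2).** Active-arm AUC = 40 × 90 = 3600. Implied SD = 3600 / 1.2 = 3000. With 24 and 12 participants, z = 1.2 / √(1/12 + 1/24) = 3.394, and power at one-sided 0.025 is Φ(3.394 − 1.960) = 92.4%, against the stated 94% or so. That is close enough to use 3600 and 3000 as the scale below; nothing here depends on the power figure.

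**1. How much Days 30 and 60 could tell us.** Assume equal correlation ρ between visits. The share of variance of the mean of the four later visits explained by Days 30 and 60 is R² = [2ρ²/(1+ρ)] / [(1+3ρ)/4].
- ρ = 0.5: 0.333 / 0.625 = 0.53
- ρ = 0.8: 0.711 / 0.850 = 0.84

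**2. One illustrative participant.** Take an active participant at −10% on both early visits, in an arm averaging −40%. With early data the predicted mean is −40 + 30 × 2ρ/(1+ρ).
- ρ = 0.5: −20.0, AUC 1800
- ρ = 0.8: −13.3, AUC 1200

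Without early data, and ignoring strata and baseline, the prediction is the arm mean, AUC about 3600. One such participant among 24 moves the active mean by (3600 − 1800)/24 = 75 to (3600 − 1200)/24 = 100 units.

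**3. Arm-level effect in ITT.** Assumptions, none from the documents: mean reduction 40% at every visit, equal correlation, dropout after Day 60 with no later Uox, and dropout odds rising by a factor e per SD of poorer Day 60 response. SD 3000 is from the plan. Imputing at the stayers' mean gives bias = dropout fraction × (mean of stayers − mean of leavers). For ρ = 0.3 and 5% dropout this is 0.05 × (3664 − 2465) = 60. For ρ = 0.9 and 20% it is 0.20 × (4070 − 1694) = 475. Simulated overstatement of the active-arm AUC, 200,000 participants per scenario:

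| ρ | 5% dropout | 10% | 20% |
|---|---|---|---|
| 0.3 | 60 | 114 | 226 |
| 0.5 | 89 | 169 | 326 |
| 0.7 | 108 | 215 | 406 |
| 0.9 | 131 | 253 | 475 |

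This is 60/3600 = 2% to 475/3600 = 13% of the planned effect. If exactly the worst Day 60 responders left, the range would be 138 to 979 (4% to 27%). With Days 30 and 60 as predictors, the bias is within about 4 units of zero in every scenario, because dropout was generated from Day 60 alone.

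**4. Day 1–180 AUC with an early value missing.** Assume 0 at Day 1, a flat 40% reduction from Day 30, and a trapezoid drawn across any gap.
- All visits: 29 × 20 + 150 × 40 = 6580
- Day 30 missing: 59 × 20 + 120 × 40 = 5980, lower by 600/6580 = 9%
- Both missing: 89 × 20 + 90 × 40 = 5380, lower by 1200/6580 = 18%
- Day 60 alone missing: 6580, no change in this flat profile

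**The case against.** The strongest reply is that this is a template, not a decision. The code is pseudo code for a general approach, it is written around the Day 90–180 endpoint, and the prose admits other visits. That stands in part: the defect is a conflict between code and prose, not a firm exclusion of early data.

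Several stronger readings are tempting, and the documents do not support them.

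- **That the primary result is biased.** Participants with only early Uox fall outside MITT, and SAP 3.5 says they do not contribute to the primary analysis. Two small effects remain. Day 60 is unused when a failed later collection is imputed. And because an efficacy assessment need not be a valid Uox, someone could enter MITT with no usable Uox from Day 90 on.
- **That everyone ITT adds is imputed without their own response.** The Day 90 urine is collected in the 7 days before that visit, so a participant who leaves afterwards has a Day 90 value in the model. An early termination visit counted as 20 to 40 days after the last visit maps to the next scheduled visit (SAP 6.1.8). Stopping drug does not mean leaving the study (Protocol 7.1). The documents give no dropout rate.
- **That the Day 1–180 AUC cannot be completed.** If Days 30 and 60 are observed, imputing the later visits completes it. The gap arises only where an early value is itself missing.
- **That the error favours DCR-PHXC.** This needs poor responders to leave more often. On-treatment Uox is withheld from investigators (Protocol 6.3), so known non-response should not drive withdrawal. Indirect links are possible, but no direction is established. The −10% participant is also hypothetical: Protocol Appendix A reports reductions of 42% to 80% after a single 3 mg/kg dose.
- **That the placebo-based model should change too.** It is fitted on about 12 placebo participants and already has 8 parameters per visit: intercept, age (2), eGFR, baseline and three other visits. Two more make 10. It would also become less conservative. An active participant at −40% on both early days would be imputed at 90 × 40 × 2ρ/(1+ρ), that is 2400 to 3200 for ρ of 0.5 to 0.8, instead of near the placebo value of 0.

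**Conclusion.** The point holds as a conflict between code and prose with limited reach. Run as coded, the ITT sensitivity analysis ignores the early response of any participant with no Uox at or after Day 90, and the Day 1–180 AUC leaves a missing Day 30 or Day 60 value unimputed.

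The first effect is an overstatement of 0.02 to 0.16 SD (60/3000 to 475/3000) in the graded-dropout scenarios. It rests on assumed correlations, dropout rates and selective loss of poor responders; without such selection there need be no bias in that direction. The second is an understatement of about 9% or 18% for an affected participant with a flat 40% reduction, if the gap is simply bridged. The SAP does not say whether it would be.

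Neither effect threatens the primary MITT conclusion. The change is still worth making before database lock, because it uses data already collected and brings the code into line with the text.

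**What to change.** 1. In SAP 6.1.5.1, add `<day 30>` and `<day 60>` to both the VAR list and the FCS REG statement of the missing-at-random model, at least for the ITT sensitivity analysis and the Day 1–180 AUC.
2. State that the placebo-based model in SAP 8.5 keeps its present variable list. That step is written as an amendment of the same code, so it would otherwise inherit the change.
3. Reconcile the ITT imputation with Protocol 9.1, under which the AUC is missing when there is no Uox after the Day 90 visit, and record the outcome in SAP 10 if it departs from the protocol.

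The cost is two more predictors in a small data set. Each visit's regression goes from 9 parameters (intercept, treatment, age (2), eGFR, baseline, three other visits) to 11, with about 36 participants. Check convergence and the spread of imputed values on blinded data, and name a fallback in advance, such as Day 60 as the only early predictor in the ITT analysis.
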